6 STUDY SETTING

For WP3, testing and optimisation study, we will recruit 5 CPs from North Central London ICS. This area includes five boroughs: Barnet, Camden, Enfield, Haringey, and Islington. We will recruit 1 CP from each borough via Pharmacy champions from the Local Clinical Research Network, North Thames (NIHR) and in person, by a research team member, if needed.

Patients will be recruited by community pharmacists following the eligibility criteria protocol. CPs will seek consent from women and deliver the two intervention components: distribute a diary (for women to complete at home) and a medication consultation at the CP. The CI will seek the transfer of Consent Forms gathered by the CPs following the Data Sharing and Transfer protocol at LMU (GDPR compliant), and the transfer of screening & enrolment logs, and demographic data. The CI and RA will contact the pharmacists and patients for a follow-up interview at each site. This is a single site type study, each delivering the same activities (as described on p8-3b). There are no specific site requirements.

7 SAMPLE AND RECRUITMENT

7.1 Eligibility Criteria

a. WP1 – 1.b Two co-design workshops:

Eligibility:

Women diagnosed with breast cancer who are,

- living in London (and)
- currently taking Hormone Therapy drugs (e.g. tamoxifen, anastrozole, letrozole, or exemestane) or had taken these drugs in the last 12 months (and)
- has/had concerns about changing medication brands.

Community Pharmacists who are,

- A pharmacist or pharmacist technician, permanent or locum (and)
- Working in pharmacies located in London (and)
- Dispensing Hormone Therapy drugs (e.g. tamoxifen, anastrozole, letrozole, or exemestane)
- b. WP1 1.c Qualitative interviews with pharmacists:

Eligibility:

- Pharmacists who are owner or manager of a community pharmacy, chain and independent;
- pharmacists with a representative role in professional pharmaceutical bodies, e.g. Local Pharmaceutical Committee, Community Pharmacy England, Royal Pharmaceutical Society. Exclusion:
- locum, technician, assistants, pharmacist not owner or manager
- Pharmacists without a representative role in professional pharmaceutical bodies
- c. WP2 2b. Qualitative interviews with pharmacists:

Eligibility:

- A pharmacist or pharmacist technician, permanent or locum (and)
- Working in community pharmacies located in London (and)
- Providing hormone therapy medication to clients

Exclusion:

- Accredited Checking Technician, assistants
- d. WP3 Testing and optimisation studies

Eligibility: Pharmacists

Inclusion

- Pharmacists and pharmacy technicians; from the London boroughs of Barnet, Camden, Enfield, Haringey, or Islington
- Providing Hormone Therapy medication to clients
- Agree to participate in online training

- Agree to recruit 4 patients from their pharmacy
- Agree to deliver a medication consultation with recruited participants and audio record 1 consultation (with patient consent), and provide feedback notes of the consultation.
- Agree to provide feedback in a study follow-up interview.
- Is willing to provide written (signed and dated) informed consent.

Exclusion:

• Locum, Accredited Checking Technician, pharmacy assistants.

Eligibility: Patients

Inclusion

- Women 18+ with early BC (stage 1-3);
- Talking oral HT medication (tamoxifen, anastrozole, or letrozole) and had/have concerns about changing HT brands;
- Not taking HT medication as neo-adjuvant or secondary metastatic BC;
- Is willing and able to record notes on side effects and medication taken (diary) and attend a medication consultation with the CP;
- Is willing and able to participate in a study follow-up interview (phone or video conference);
- Is willing to provide a copy of the diary;
- Is willing to be audio recorded during the pharmacy consultation;
- Is willing to provide written (signed and dated) informed consent.

Exclusion

- Male
- Currently or recently (last 6 months) involved in another research study where medication adherence is a primary outcome;
- Have had in the last 6 months a medication review about changing brands of HT drugs.

The target population will comprise women with greatest potential to benefit clinically from HT: women with early stage (1-3) ER-positive breast cancer. The evidence-base for this study, our primary research, and the PAG who provided feedback, consist of women with BC. Its suitability for men is not known, therefore, men will be excluded. Proficiency in English is not a requirement, we will facilitate translations and interpreters from our Language team (LMU) for common languages spoken in the boroughs. We will be guided by pharmacists' requests.

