1 BACKGROUND

Breast cancer (BC) is the most common cancer in the UK, with an estimated 55,900 new cases diagnosed in women every year [1]. Around 80% of BCs are oestrogen receptor positive, which means that for the great majority of BC survivors, treatment does not end with surgery, radiation and/or chemotherapy. Hormone therapy (HT) drugs (tamoxifen, letrozole, anastrozole, and exemestane) are prescribed for 5 to 10 years to reduce the risk of recurrence and mortality. These drugs are known to cause several side effects and have been consistently identified in the literature as a key factor of nonadherence [2] and poor quality of life (QoL) [3]. By the fifth year of treatment, adherence to HT is suboptimal, estimated between 41%-72% and treatment continuation between 31%-73% [4]. In the UK, it is common practice for community pharmacies (CPs) to dispense a different generic of the same drug when patients collect their prescriptions. Currently, the British National Formulary lists 10 generics for tamoxifen, 10 for letrozole, 17 for anastrozole and 13 for exemestane, in addition to their proprietary names [5]. Clinical studies on women's experiences with HT medications revealed that the use of generic drugs either to replace the proprietary name (generic substitution) or to switch amongst generic brands (generic switching) can have a negative impact on patients' side effects. attitudes and acceptance of certain generic brands [6-7]. In women switching tamoxifen generics, a small but significant number of patients (11-13%) attributed severe menopausal symptoms to brand switch, which stopped when taking a different brand. Authors considered that patients' perceived change in medication side effects was due to manufacturers' use of different excipient profiles [6-7]. Additionally, experimental studies have shown that patients often misattribute symptoms (emerging from everyday activities, disease or environmental factors) as medication side effects [8], raising the need to assist patients in recognising drug-related symptoms. Both experiences of new side effects (excipient-related or beliefs-induced) can hamper BC patients' QoL and treatment continuation. Our previous study of medication brand changes (MBC) confirmed that a significant minority of BC patients have a negative experience when they receive a different generic drug, reporting new side effects, phycological impact, lack of information on generics, feeling unsupported, disbelief about symptoms from healthcare professionals, and concern about quality and effectiveness [9]. These medication concerns undermine patients' self-efficacy (skills and confidence) for medication-taking behaviours and have an impact on adherence and persistence [6-7,9-10].

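### The WP3 patient criterion lists three hormone-therapy drugs and leaves out exemestane, which the Background and the WP1 criteria include; no reason is given

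*Protocol*

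**What the plan says.** Section 1 (Background) sets out the treatment class: "Hormone therapy (HT) drugs (tamoxifen, letrozole, anastrozole, and exemestane) are prescribed for 5 to 10 years". To show how often a brand change can arise, it then counts the available products: "10 generics for tamoxifen, 10 for letrozole, 17 for anastrozole and 13 for exemestane".

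Section 7.1 (Eligibility Criteria) gives a drug criterion for each work package:

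- WP1 workshops, patients: "currently taking Hormone Therapy drugs (e.g. tamoxifen, anastrozole, letrozole, or exemestane) or had taken these drugs in the last 12 months".
- WP1 workshops, pharmacists: "Dispensing Hormone Therapy drugs (e.g. tamoxifen, anastrozole, letrozole, or exemestane".
- WP2 interviews, pharmacists: "Providing hormone therapy medication to clients". The WP3 pharmacist criterion is the same apart from capital letters.
- WP3, patients: "Talking oral HT medication (tamoxifen, anastrozole, or letrozole) and had/have concerns about changing HT brands".

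The paragraph that closes section 7.1 describes the WP3 target population as "women with early stage (1-3) ER-positive breast cancer" and explains why men are excluded. It says nothing about choice of drug. Section 7.3, part d, has pharmacists approach women who come to collect a hormone-therapy prescription, again with no drug named.

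**The concern.** Two WP1 criteria name four drugs and introduce them as examples. The WP3 patient criterion, in the same section, names three and does not present them as examples. A pharmacist who applies it as written must decline a woman taking exemestane, although she fits the target population described a few lines later.

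The wording matters in practice because the research team does not do the screening. Under section 6, community pharmacists recruit according to the eligibility criteria, and under section 7.3 they record screening in a log. Five pharmacists faced with an unexplained three-drug list may also read it differently from one another.

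What is at stake is the coverage of the acceptability findings. Section 5 (WP3, parts 3b and 3c) makes this the one stage in which patients keep the diary and attend the consultation. Its findings identify the core materials and processes of ENABLE and feed the feasibility protocol. Under the present wording, none of that feedback could come from a woman on exemestane.

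**Working it through.** The check is a comparison of texts. The plan has no figure to reproduce on this point.

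**Step 1: every place that sets a drug scope.**

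| Place in the Protocol | Drug scope | Exemestane |
|---|---|---|
| Section 1, treatment class | four drugs named | included |
| Section 1, count of generics | four drugs counted | included |
| Section 7.1 a, WP1 patients | four drugs, as examples | included |
| Section 7.1 a, WP1 pharmacists | four drugs, as examples | included |
| Section 7.1 c and d, WP2 and WP3 pharmacists | hormone therapy in general | not excluded |
| Section 7.1 d, WP3 patients, inclusion | three drugs, closed list | **absent** |
| Section 7.1 d, WP3 patients, exclusion | no drug named | not excluded |
| Section 7.1, target-population paragraph | stage and receptor status only | not excluded |
| Section 7.3 d, WP3 recruitment | any hormone-therapy prescription | not excluded |

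The scope narrows in one place only.

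**Step 2: is the narrowing explained?** Section 7.1 justifies early-stage disease and the exclusion of men. Section 7.2 justifies the sample size. Neither mentions drug, and no other section supplies a reason. The text does not show whether the omission is deliberate or a drafting slip.

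**Step 3: what the generic count does and does not show.** 10 + 10 + 17 + 13 = 50 listed generics. Exemestane has 13, and 13/50 = 26%. This shows that the protocol itself treats exemestane as part of the brand-change problem: it lists more generics for it than for tamoxifen (10) or letrozole (10). It is a share of products and says nothing about the share of women, prescriptions or switches.

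**Step 4: effect on the sample.** The target is 5 pharmacists × 4 patients = 20, whichever list is used. No places are lost; only the possible mix of drugs changes.

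**Step 5: would an open list bring in exemestane users?** The protocol gives no share of patients on exemestane. Suppose, purely as an assumption, that a fraction p of otherwise eligible women take it and that enrolments are independent. The expected number among 20 is 20p, and the chance of enrolling none is (1 − p)^20.

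- p = 5%: expected 20 × 0.05 = 1; chance of none 0.95^20 = 36%.
- p = 15%: expected 20 × 0.15 = 3; chance of none 0.85^20 = 4%.

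Under the closed list, applied literally, the chance of none is 100% by construction. Opening the list permits feedback from exemestane users but does not guarantee it, since WP3 has no quota by drug.

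**The case against.** The strongest reply is that this is a wording slip with little consequence. The intervention is not described as drug-specific. The diary records side effects and life events, and the consultation guide deals with communication, attribution of side effects and problem-solving. No analysis by drug is planned; the subgroup interest in section 5 is demographic. Nothing shows that feedback on the diary or on a 10-minute consultation would differ for a woman on exemestane. Section 7.2 also leaves a powered assessment of acceptability to the later feasibility study, so WP3 is not the last opportunity to include these women.

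Much of this stands, and it limits the weight of the point. It does not remove the contradiction, because nothing in the protocol explains or resolves the three-drug list, and pharmacists are asked to screen by it.

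A reader might infer more than the documents support:

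- *That the materials are co-designed with exemestane users.* The workshops are open to them, but the 10 patients are sampled on sociodemographic characteristics (section 7.3 a), and nothing says that an exemestane user will attend.
- *That exemestane is a declared target drug of ENABLE.* The aim, objectives and outcome (section 4) name no drug. Exemestane comes in only through the Background and the WP1 criteria.
- *That the feasibility study will cover all four drugs.* That protocol is a future output, and its drug scope is not stated.
- *That about a quarter of eligible women are shut out.* The 26% counts products.
- *That recruitment is put at risk.* A narrower list can only shrink the pool, but by how much cannot be worked out from the protocol.

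**Conclusion.** The inconsistency is real and unexplained: one eligibility criterion is narrower than the Background, the WP1 criteria, the stated WP3 target population and the WP3 recruitment text. Applied literally, it excludes otherwise eligible women on exemestane from the only stage that tries out the diary and consultation.

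The size is modest. WP3 is a 20-patient qualitative test; no sample size, power or error rate changes, and the number of women affected cannot be derived from the protocol. The conclusion rests on reading the WP3 list as complete, which its wording supports, and on pharmacists applying it as written. It does not rest on the assumed 5% to 15% range, which serves only to show that a wider list would not by itself ensure that exemestane users enrol. The passages should be reconciled before WP3 screening, but the point does not undermine the study.

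**What to change.** Reconcile the WP3 patient criterion in section 7.1 d with section 1 and the WP1 criteria by using the same hormone-therapy drug list. Carry the wording into the WP3 screening log and patient information sheet if they name drugs; both are listed in Appendix 1 but are not shown, so this needs checking.

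If the narrower list is deliberate, state the reason in section 7.1. Then limit the WP3 acceptability conclusions, and what is carried into the feasibility protocol, to the drugs tested.

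In either case, report the mix of drugs among the patients enrolled, so that readers can see which users gave the feedback. Section 7.3 d already has pharmacists record the medication taken, so this needs no new data.

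The cost is a short amendment. Under section 8.2, changes to documents that needed REC approval must wait for that approval and for HRA categorisation, so it should be submitted in time for screening. The sample stays at 20.

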7.2 Sampling

a. WP1 – 1.b Two co-design workshops:

We will purposively sample 10 BC patients and 10 community pharmacists.

b. WP1 - 1.c Qualitative interviews with pharmacists:

A purposive stratified sample of 10 pharmacists: 6 from Community Pharmacies (3 chain; 3 independent) and 4 from professional pharmaceutical bodies. For the latter, snowball technique may also be used.

c. WP2 - 2b. Qualitative interviews with pharmacists:

Between 8-10 community pharmacists will be purposively sampled. We will seek their feedback after testing the e-learning package.

d. WP3 - Testing and optimisation studies

A purposive sample of 5 community pharmacists [2 located in the 20% IMD], and 20 patients.

Sample size: the overall approach to sample size for intervention development studies, following the Person-Based Approach [36], is to collect feedback from target users and stakeholders iteratively, at different stages in the development process. The development of intervention ingredients and content will include 2 workshops of 20 target users each (patients and pharmacists) involved as PPIE (public contributors). This will be followed by three instances of qualitative feedback from research participants in the samples provided above. This is a different form of sample size estimation to the one observed in stand- alone qualitative studies, in that the first intervention prototype is being modified by target users at different stages. Finally, for the testing stage, given the nature and organisational requirements of the intervention, it is not possible to recruit participants until reaching data saturation on its acceptability. This will be further explored in a future feasibility study, with a sample size calculation and sufficiently powered to analyse acceptability and feasibility.

7.3 Recruitment

a. WP1 – 1.b Two co-design workshops: Patients: We will recruit women in London with different sociodemographic characteristics (age, ethnicity, language and socioeconomic status). Evidence indicates that BC incidence rates are lower (7%) in non-White British women [55]. However, women's care experiences in minoritised ethnic groups are comparatively lower than Whites [56], whilst intentional non-adherence to HT drugs is higher than Whites [29]. There is also evidence that younger and older age, and deprivation are factors influencing non-adherence [29]. As these groups might benefit from the intervention, our recruitment approach will draw on two strategies; 1) inviting participants through organisations representing minoritised groups: Brest Cancer Now, Bric Centre, Race on the agenda [ROTA], Black Women Rising, South Asian Health Action, and others representing Turkish and Arabic communities prevalent in the study area, and 2) monitoring of recruitment to focus on particular characteristics not reflected in our criteria. The PIS form will be explicit about the need to capture a plurality of voices from people with different backgrounds, the limited numbers, and the selection process prior acceptance of participants. Our PPIE-lead will monitor this task.

Organisations will post invitations (English and translated) with a link to the PIS through a newsletter (email), social media (Tweeter, Instagram, Facebook), and/or webpage. We will also attend community venues of relevant local ethnic groups to promote the study and its benefits to patients, and seek their advice on the best form of communication. Contact with patient groups within GP practices and snowball technique will also be used as recruitment methods. The PIS will describe the nature of the study, details of the 2-day in-person workshop participation requirement, payment offered, a link to access the registration form (OneDrive) or printed copy, and an email to contact the research team for further information. Interested women will complete a registration form about their preferred way of contact, confirm their HT medication taking status, age, ethnicity, and post code (for IMD identification). Those registered will be notified on whether they have been selected or not based on recruitment criteria. Those who registered and could not attend in person, will be offered the opportunity to contribute online to the workshop they have missed. Selected patients will sign an informed consent form prior attendance via a 'simple' electronic signature, or by bringing a signed paper copy to the workshop.

Community Pharmacists: Recruitment will take place via newsletter (email or website) distributed by Local Pharmaceutical Committee networks in London. PIS will describe the nature of the study, details of the 2-day workshop participation requirement, a certificate (for use as CPD portfolio), payment

offered, a link to access the registration form (OneDrive), and an email to contact the research team for further information. At registration, interested pharmacists will be asked about their preferred way of contact, job title, years of work experience, and CP post code (IMD). The latter will ensure we include representatives from different boroughs, occupations, work experience, and different SE areas. Similarly to our patients' PIS, those registered will be notified on whether they have been selected or not. Those who registered and could not attend in person, will be offered the opportunity to contribute online to the workshop they have missed. Selected pharmacists will sign an informed consent form prior attendance via 'simple' electronic signature.

All workshop participants will be offered a £75 voucher p/workshop, travel expenses and lunch. Pharmacists attending in person will be offered a reimburse for locum backfill for 4 hrs.

b. WP1 - 1.c Qualitative interviews with pharmacists: To ensure representation from deprived communities, we will recruit 3 community pharmacists servicing these areas. We will use our existing contacts with Local Pharmaceutical Committee networks and Pharmacy champions from the Local Clinical Research Network, North Thames (LCRN) to advertise via website, newsletter or social media (*Appendix: WP1- Leaflet Pharmacy interviews [owners or managers]*); and professional bodies (Local Pharmaceutical Committee, Community Pharmacy England, Royal Pharmaceutical Society) to obtain a list of potential participants. PIS and consent forms will be available and stored in our OneDrive study folder (*Appendix: WP1- Pharmacist staff & Professional bodies – PIS and Consent forms*). A 'simple' electronic signature will be required prior to the interview. Pharmacists will be offered a £30 voucher for their interview time with the research team.

c. WP2 - 2b. Qualitative interviews with pharmacists: Pharmacists participating in workshops [point a.] will be invited to test the e-learning package and provide feedback. If more participants are needed, they will be recruited in the same way as described for the workshops, via leaflet (email or website) distributed by Local Pharmaceutical Committee networks in London, and in person visits to CPs by our research team (*Appendix: WP2- Leaflet Pharmacy feedback*). PIS and consent forms will be available in our OneDrive study folder, and a 'simple' electronic signature will be required prior to the interview (*WP2-Pharmacist feedback PIS and Consent form*). Pharmacists who take part in testing and interviews will be offered a certificate (CPD) and a £75 voucher as a thank you for their time.

d. WP3 - Testing and optimisation studies: Pharmacists: We will recruit 5 CPs, one for each borough, and from different socio-economic areas, including 2 in the bottom 20% by IMD, serving diverse ethnic minority groups to maximize intersectional contrasts in our analysis. We will send invitations to participate through Pharmacy champions LCRN and in person (if needed) to meet our recruitment criteria (*Appendix: WP3 - Leaflet invitation Community Pharmacies*). We will seek permission from the pharmacy's Head office or owner before approaching a pharmacy. Once permission is granted, we will invite the pharmacy staff to the study with the PIS, explaining all its components (training, recruitment, medication consultation, feedback forms, and interview) (*Appendix: WP3 - Pharmacist PIS & Consent form*). Pharmacists interested in taking part will have at least 24 hours to decide whether or not to take part, and will hand in their written Consent forms to the CI. Pharmacy organisations will receive a small expenses fee for participating in the study of £1,100 (time incurred in online training, recruitment, medication consultation). Pharmacists will be offered a £30 voucher for their follow-up interview time with the research team.

Patients: Trained pharmacists will recruit 4 BC patients each, from their CPs, during a 2 month-period. Women will be approached opportunistically, when collecting their HT prescription. If pharmacies consider it necessary to facilitate recruitment, they will be able to put a poster about the study, visible to the public, inviting interested women to approach the pharmacy staff for information (*Appendix: WP3- Poster Community Pharmacy 1&2*). This will target patients who might be willing to participate but are not collecting a HT prescription within the recruitment time frame.

Pharmacists will ask potential participants if they would be interested in taking part in a study about discussing with pharmacists concerns with HT medication brand changes. If patients accepted, the pharmacist will ask each patient to answer a few questions (*Appendix: Participant Screening and Enrolment log*). Eligible patients will be provided with a PIS and the informed consent form (*Appendix: WP3- Patient PIS & Consent Form*). At least 24 hours after the receipt of the PIS, the pharmacy will telephone the woman, answer any questions and, if she wishes to take part, ask her to bring the signed consent form to the pharmacy. It should be noted that if a woman is happy to be consented immediately, and the pharmacist is satisfied the woman has fully comprehended what is being asked of her, then consent can be taken immediately. Mental capacity will be assumed unless proven otherwise. When women return their consent form, they will receive a diary from the pharmacist, who will also collect simple demographic data [post code, age, ethnicity, medication taken, education, living alone or with family, work status and email or prefer contact for arranging medical consultation] (*Appendix: WP3-Participant demographic information*). Each patient will be assigned an ID number by the pharmacist.

Pharmacists will be able to recruit women who are not fluent in English, and with whom they communicate in another language. The most common languages used in the area are Turkish, Arabic and Bengali. If the pharmacist consider that such women might be able to participate, we will provide translated PIS and consent forms. If the woman accepts to take part in the study, we will provide a translated copy of the diary for her to complete.

To this aim, we will first contact LMU Translation Department staff to identify a translator with a Diploma in Public Service Interpreting – Health (DiPS-H) – as recommended by the NIHR. If need be, we will engage with our host organisation (NCL ICB) to put us in contact with specific translators.

For the interviews, a female DiPS-H translator and interpreter will help us communicate as follows:

- translate the diary entries
- translate our email correspondence to arrange an interview.

- translate the key questions we are interested in asking for the interview – so patient and interpreter know content in advance.

- attend the interview to simultaneously interpret for the participant and interviewer.

To protect the participant's privacy in our correspondence with the translator, we will copy the participant using a blind copy.

Patients will be offered a £30 voucher for their follow-up interview time with the research team.

Patient Advisory Group (PAG):

It will comprise a group of 5 women with BC, taking HT, who have experienced concerns about changing medication brands. Three members of this group provided feedback on early stages of this study and have expressed willingness to continue. Recruitment: 2 members will be recruited from minoritised ethnic groups living in London. This is to ensure representativeness as the existing members are White British, age range (35-72) based in England.

We will advertise the PAG role in the patient organisations already mentioned, using the Cancer Research UK patient involvement registration form, whereby interested applicants are invited to an interview. This is to explain the work involved and the importance of commitment for 20 months. Meetings will take place online to facilitate issues with time, patients' mobility, and costs. PAG members will receive payment for their time in line with NIHR INVOLVE recommendations.

